identified locations. All data collection activities will comply with the recommended social distancing requirements currently in place at the time.

Quantitative study measures will be implemented through the use of on-line REDCAP survey software and is available to interested individuals through an on-line link. Participants can complete the survey in any environment in which they have access to the Internet (i.e., public library; home; work). If the interested participant does not have a device to access the Internet and the survey or communicate with the researcher to indicate their responses, the primary researcher will meet them a place identified as convenient for the participant with the necessary equipment to complete the survey (i.e., laptop computer with Internet connectivity).

8) Prior Approvals

N/A

9) Study Design

Recruitment Methods

Recruitment will occur through local community partners, which include Philadelphia Independence Network, Community Integrated Services, Carousel Connection GRASP, ASERT, Philadelphia the Institute of Disability at Temple University, and the Philadelphia Area Charter School. We have an established relationship with all of these organizations. An introductory recruitment e-mail (see materials submitted with IRB protocol) will be sent to potential participants through the organization, which includes a link to the survey questions on REDCAP.

Phase 1

We intend to recruit 20 employed individuals with ASD and 20 employed individuals with IDD to complete in depth qualitative interviews, 100 employed individuals with ASD and 100 employed with IDD to complete **quantitative** perceptual mapping surveys. We will recruit 40 individuals 10 ASD 10 IDD, 10 vocational staff, and 10 from the project Advisory Board to conduct vector modeling analysis with and complete sample messaging. We aim to recruit at least 120 participants with ASD and 120 participants with IDD for the pilot SAFE program, which we anticipate will yield a total of 96 participants in the final sample when accounting for 20% attrition rates commonly identified in prior intervention studies of people with ASD and/or IDD.

Phase 2

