We will recruit 60 individuals—30 with IDD and 30 vocational staff—to participate in focus groups aimed at identifying stakeholder priorities for additional health communication related to staying safe from infectious airborne diseases and ensuring workplace safety. Focus groups will ideally include 5-10 people, but that they may be as small as 1, thus turning it into an interview instead.

The project team will recruit 5-10 staff members from community partners listed above to participate in a pilot training session. Following the training, staff

SAFE Protocol

member participants will provide feedback to inform any necessary revisions to the training materials or processes, ensuring the content is effective and practical for future use. The additional lessons will be developed based on feedback from the focus group. Once completed, the materials (including recruitment materials) will be submitted as an amendment to the IRB and will not be used until approval is granted. After IRB approval, the materials will be provided to the staff and used in the training.

This will require between 2-3 one to two hour sessions.

a) Inclusion and Exclusion Criteria

We anticipate recruiting young adults 18 years old and over with ASD or IDD who are currently employed or actively looking for employment to participate in the study. Participants will have a diagnosis of ASD or IDD. Participants will self-report their ASD or IDD diagnosis. Additionally, the community agencies have access to documentation that identifies their consumer's diagnoses. Based on this, we will ask them to only provide information to those individuals who have a diagnosis of IDD. Potentially eligible participants with documented intellectual and developmental disabilities will be recruited through large vocational rehabilitation organizations (Community Integration Services [CIS] and Project Search) that together serve over 1200 adults with IDD. Participants must be working a minimum of 10 hours a week outside the home and/or receive vocational rehabilitation services. We aim to recruit at least 120 participants, which we anticipate will yield a total of 96 participants in the final sample when accounting for 20% attrition rates commonly identified in prior intervention studies of people with ASD/IDD.

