We intend to complete the **SAFE program** and interviews over the course of three years starting as soon as IRB approval is obtained. We intend to complete the qualitative interviews and quantitative surveys in the first year. We intend to implement the SAFE program until approximately 120 participants have completed the program and data collection during year two and three. Recruitment will occur throughout the course of the study until the targeted number of participants is obtained. We will use block randomization, which will allow us to have continuous enrollment in the study.

Participation in the **SAFE program** is completed over the course of 2-4 weeks.

Participants will meet 2-3 times a week for approximately 60 minutes with either staff, a peer support specialist peer, or occupational therapy graduate students. The meetings will provide direct instruction and role play experiences covering the main concepts and proper use of preventable behaviors to protect against COVID-19 and other airborne diseases in the workplace.

Phase 2

Phase 2 will be completed over the course of one year following IRB approval. During the first two months, recruitment for the focus groups will take place. In months 2-4, focus groups will be conducted, and their feedback will be analyzed. Months 4-8 will involve revising the SAFE curriculum by adding lessons based on the focus group feedback. The final months will focus on recruitment and training.

Study Procedures and Data Analysis

Procedures.

To assess perceptions of peer-support interventions and use of preventative decision-making practices for individuals with ASD and or IDD in the workplace we will conduct in-depth qualitative interviews with individuals with ASD and or IDD working 10 hours or more a week (n=20 or until data saturation) who receive employment services or supports in order to: 1) understand the barriers and facilitators of implementing preventative decision-making practices for IADs and individuals with IDD in the workplace; 2) examine the perceptions and acceptability of peer support intervention strategies; and 3) develop a perceptual mapping survey instrument based on these findings.

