If the participant is assigned to the staff intervention support staff will be contacted with an email or phone call. Staff members will be required to complete human subjects training. Researchers will obtain informed consent for all participants. During the first contact made with participants, written information will be provided remotely using Zoom/FaceTime or in person to all participants explaining the following in simple terms: 1) the criteria for participation, 2) the purpose of the research and the procedures involved, 3) the subject's right to withdraw at any time without penalty of any sort, 4) potential benefits to the subject, 5) potential risks, 6) assurance of anonymity, and 7) terms of remuneration. All research staff will complete training about the informed consent process prior to consenting subjects. The information described above will be reviewed and any questions answered. Participants will be obtained signed or a printed signature box used for signature when electronic signatures are unable to be obtained for consent either in person or virtually.

We will collect data from young adults or transitional aged-youth with ASD or IDD to determine the efficacy and feasibility of the intervention. Recruitment occurs through the sites identified in the participant recruitment section of this proposal. Participants interested in the study will contact the primary investigator or research staff who will schedule an initial physical or virtual meeting at a place and time convenient for the participant to determine inclusion and obtain consent/assent. Participants are randomly assigned to either peer-support intervention, staff intervention or a control group. We will randomize in blocks of 12 (4 to each group) until we reach the targeted number of 120 or

SAFE Protocol

40 participants in each group. Pre-test and post-test measures will be administered by researcher staff prior to the start of the intervention (Pre-test) and at the end of the intervention 4 weeks (Post-test). Key stakeholders, including the participants and interventionists (occupational therapists and peer mediators), will complete qualitative interviews at the end of the intervention period for each participant. The information gathered will determine acceptability and feasibility of intervention. Participants will be asked to discuss their experiences during the intervention specific to their assigned intervention group.

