A member from the research team will then contact interested individuals to set up a convenient meeting time and place for the **SAFE** program training. These meetings will occur remotely or in a private location convenient to the participant. The **SAFE** program course training will occur in small group settings or individually. The course trainings will occur 2-3 times per week for between 45-60 minutes. An appropriate curriculum has been developed by Temple University Researchers and Occupational therapy students based on many qualitative interviews, research of proper education methods, and COVID-19 practices. The curriculum is based on a series of classes designed to create an understanding of best practices and behaviors to prevent the spread of COVID-19 in the workplace. The curriculum will be adapted to meet the needs of this project and study population. The course will provide instruction in the following areas: 1) COVID-19 and how it spreads 2) PPE and How to use it properly 3) Social Distancing 4) Community Participation 5) Employment 6) Self Efficacy.

Participants will complete the **SAFE** program sessions remotely or in person in a private, quiet and convenient setting.. Participants will be randomized into two treatment arms and a control group. The first treatment arm will receive the **SAFE** program implemented through a staff training model. The second group will receive the program using a peer support model. The control group will continue to receive their standard vocational rehabilitation supports.

Training of the **SAFE** program will occur remotely or person by staff who are trained within our research team or we will implement it in collaboration with staff or a peer specialist remotely as part of their current services. If it is in person it will be implemented at their vocational rehabilitation centers or places of employment. Research staff will be available to support the process after the training is complete.

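### The pilot sample-size sentence in Recruitment Methods does not add up: 240 recruited at 20% attrition leaves 192, not 96, and 240 is twice the total given elsewhere

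*Combined protocol and SAP*

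**What the plan says.** Four places in the combined protocol and SAP give numbers for the randomised pilot.

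- **Section 9, Recruitment Methods, Phase 1.** The target is set by diagnosis: "We aim to recruit at least 120 participants with ASD and 120 participants with IDD for the pilot SAFE program". The sentence goes on: "which we anticipate will yield a total of 96 participants in the final sample when accounting for 20% attrition rates".
- **Section 9a, Inclusion and Exclusion Criteria.** Nearly the same sentence appears without the split by diagnosis: "We aim to recruit at least 120 participants, which we anticipate will yield a total of 96 participants in the final sample". The attrition allowance is again 20%.
- **Study Procedures and Data Analysis, Procedures.** There are three groups (peer support, staff, control), and the plan is to "randomize in blocks of 12 (4 to each group) until we reach the targeted number of 120 or" "40 participants in each group".
- **Section 9b, Study Timelines, Phase 1.** The program is to run "until approximately 120 participants have completed the program and data collection during year two and three".

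The documents contain no power calculation: no significance level, power, effect size or standard deviation is given for any outcome.

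**The concern.** The Recruitment Methods sentence fails on its own terms, because its recruitment figure, attrition rate and yield cannot all be true. It also gives a recruitment total that differs by a factor of two from the totals in section 9a and Procedures.

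With no power calculation, these counts are the only sample-size basis that the plan offers for the three-group comparison. Someone reading only Recruitment Methods would plan for 240 people; someone reading Procedures would stop randomising at 120. The plan should state one total, with a yield that follows from it.

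**Working it through.** **Inputs.** Recruited, by diagnosis: 120 with ASD and 120 with IDD (Recruitment Methods). Recruited, overall: 120 (section 9a). Attrition: 20% (both). Stated final sample: 96 (both). Randomisation: blocks of 12, 4 per group, to 120 or 40 per group, three groups (Procedures). Timeline count: about 120 completing (section 9b).

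**Formula.** Final sample = recruited × (1 − attrition).

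**1. Reproduce the plan's 96.**
- From 120: 120 × (1 − 0.20) = 96, exact. In reverse, 96 / 0.80 = 120.
- From 240: 240 × (1 − 0.20) = 192, which is twice 96.
- Applying the allowance the other way does not rescue it: 240 / 1.20 = 200.
- Attrition needed to reach 96 from 240: 1 − 96/240 = 0.60, or 60% against the stated 20%.

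So 96 comes only from a total of 120.

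**2. Compare with the randomisation target.**
- 3 groups × 40 = 120, and 120 / 12 = 10 complete blocks. Procedures is internally consistent.
- 240 / 120 = 2, so Recruitment Methods gives double the number to be randomised.
- With 120 randomised and equal attrition across groups, 96 / 3 = 32 are expected to complete per group.

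**3. What 240 would imply if intended.**
- 240 / 12 = 20 blocks and 240 / 3 = 80 per group.
- 192 completing in total, which is 96 per diagnosis, or 192 / 3 = 64 per group with equal attrition.
- None of these totals or per-group figures appears in section 9a, section 9b or Procedures.

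**4. The section 9b count.**
- Taken literally, 120 people completing at 20% attrition requires 120 / 0.80 = 150 recruited.
- Neither 120 nor 240 recruited gives 120 completing: the yields are 96 and 192.

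**The case against.** **The two diagnoses could overlap, so that 120 and 120 need not sum to 240.** The sentence before the pilot target counts against this. It describes 40 people made up of 10 with ASD, 10 with IDD, 10 staff and 10 advisory board members, and 10 + 10 + 10 + 10 = 40 only if the diagnoses are added as separate groups.

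**The 96 could be meant per diagnosis.** That would repair the arithmetic (120 × 0.8 = 96 for each). But the sentence calls 96 a total, and the reading would still conflict with section 9a and Procedures.

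**It is a drafting slip and the randomisation rule is clear.** Much of this stands. Procedures gives an unambiguous target, and section 9b says separately that recruitment continues until the target number is reached. A reader might infer that enrolment has no stopping rule; it has one. The section 9b phrase about completion may simply be loose wording for 120 enrolled. It is qualified as approximate, and it cannot literally describe 120 people completing the program under the Procedures allocation, since "The control group will continue to receive their standard vocational rehabilitation supports" and only 2 × 40 = 80 are allocated to the program.

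**Stronger readings that the documents do not support:**
- *That Recruitment Methods doubles pooled counts by mistake throughout.* Its interview and survey numbers are larger than some pooled numbers in Procedures, but the evidence is mixed. The interview count is open-ended ("working 10 hours or more a week (n=20 or until data saturation"). The survey analysis text mentions 150–200 people. The concept-testing paragraph lists 10 with ASD and 10 with IDD, where an earlier paragraph has a pooled 10. Partial updating towards targets by diagnosis is as possible as accidental doubling, so these counts do not decide the pilot total.
- *That the feasibility result would change from full success to a half-miss.* The Feasibility Data paragraph lists recruitment and retention rates as benchmarks, but gives no threshold and no denominator. Any such percentage would be the reader's own construction.
- *That the trial is under-powered.* Without a power calculation, the effect of 96 against 192 completing on power cannot be assessed.

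**Conclusion.** The point holds. The Recruitment Methods sentence is wrong as written: its own inputs give 192, twice the stated 96, and its recruitment total of 240 is twice the 120 in section 9a and Procedures. No reading of the sponsor's intention makes 240 people at 20% attrition equal 96, so the sentence must change either way.

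A total of 120 is the better-supported reading, because section 9a and Procedures agree with each other and 96 follows from 120 exactly. That is a judgement from consistency; the documents do not state which total was intended. The figure of about 32 completing per group also assumes that attrition is equal across groups.

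The section 9b mismatch (about 120 completing against 96 expected) is secondary and may be wording only. The correction is worth making because these are the only sample-size figures for the comparison, but it does not show that the allocation scheme is unsound.

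**What to change.** The sponsor should first confirm the intended total.

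**If 120 in total (the reading supported by section 9a and Procedures).** Replace the pilot sentence in Recruitment Methods with wording such as: *The pilot will enrol a minimum of 120 people overall, each with ASD or IDD. Allowing for 20% attrition, 96 are expected in the final sample (40 randomised and about 32 expected to complete in each of the three groups).* Describing the 32 as expected to complete, rather than as analysed, avoids writing a completers-only analysis into a plan that does not specify one. The cost is a wording change, with no added participants.

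**If 120 per diagnosis.** State the yield as 96 per diagnosis and 192 in total, and change sections 9a, 9b and Procedures to match. Against the present randomisation target this adds 240 − 120 = 120 participants, with the recruitment time and budget that they need.

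**In either case, section 9b.** Align the completion phrase with the confirmed figures. If it means the 120 randomised in Procedures, it should say so. If 120 completing is really meant, the recruitment figure would have to be 150 at 20% attrition, and the other sections would need to change accordingly.

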The participants must have communication skills or a system to engage in the learning process, which will be determined during the initial meeting and assessment. All participants must speak English. For those participants who are nonverbal, visual and communication systems can be used, although participants must be able to cognitively answer questions on their own and provide consent/assent. These devices can also be used during the initial interview process to provide yes or no answers to formal interview questions. Participants with ASD or IDD can have assistance completing the questionnaire if they need help in reading and understanding the questions or checking the appropriate answer box. For any participants that are not able to participate in the SAFE program methodology or qualitative interviews, a support staff, parents or caregiver proxy can be used.

Phase 2

For phase 2, we will recruit young adults aged 18 and over with ASD or IDD who are currently employed or seeking employment, as well as staff who support young adults with ASD or IDD in employment settings. Participants must either self-report their diagnosis. Additionally, community agencies have access to documentation that identifies their consumer's diagnoses and, based on this, research personnel will ask them to only provide information to those individuals who have a diagnosis of IDD. Recruitment will occur through large vocational rehabilitation organizations that serve over 1,200 adults with IDD. Eligible participants must work at least 10 hours per week

SAFE Protocol

and/or receive vocational rehabilitation services. We aim to recruit 60 participants. All participants must have communication skills or systems to engage in the focus groups and be able to provide consent.

Project team members will include 5-10 staff members from a selected service provider organization to participate in a pilot training session. Staff will directly support young adults with IDD with their employment goals.

b) Study Timelines

Phase 1

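### The Phase 1 instruction to recruiting agencies names only an IDD diagnosis, although people with ASD are eligible and have recruitment targets of their own

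*Combined protocol and SAP*

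**What the plan says.** On eligibility, section 9 a) Inclusion and Exclusion Criteria states: "Participants will have a diagnosis of ASD or IDD". Diagnosis is self-reported, and the agencies are noted to hold diagnostic documentation as well. Three sentences after the eligibility statement comes the instruction built on that documentation: "we will ask them to only provide information to those individuals who have a diagnosis of IDD". The next sentence also describes recruits as having documented intellectual and developmental disabilities, without naming ASD.

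On targets, section 9 Recruitment Methods (Phase 1) lists ASD and IDD as separate groups:
- interviews: "We intend to recruit 20 employed individuals with ASD and 20 employed individuals with IDD to complete in depth qualitative interviews"
- perceptual mapping survey: "100 employed individuals with ASD and 100 employed with IDD to complete"
- vector modeling and sample messaging: "We will recruit 40 individuals 10 ASD 10 IDD, 10 vocational staff, and 10 from the project Advisory Board"
- pilot: "We aim to recruit at least 120 participants with ASD and 120 participants with IDD for the pilot SAFE program"

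On who is to be told, Study Procedures and Data Analysis says twice that organizational administrators pass study information to people who satisfy the inclusion criteria. One statement is in the paragraph on interviews and focus groups, the other in the paragraph on the perceptual mapping survey.

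For Phase 2, the criteria again admit ASD or IDD and again say that "research personnel will ask them to only provide information to those individuals who have a diagnosis of IDD". The Phase 2 focus-group target in Recruitment Methods is 30 people with IDD and 30 vocational staff.

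**The concern.** The agencies are the main way in: the introductory e-mail goes to potential participants through the partner organizations. An agency that searches its files for an IDD diagnosis, as the criteria section asks, would pass over a client whose only diagnosis is ASD. Self-report cannot correct this, because a person who is never told of the study never reports a diagnosis to it.

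The ASD places would then fill from people who hold both diagnoses, or by some other route. The sample would differ from the one described. So would the population to which the survey maps, the messages and the pilot results apply. This matters because the objectives name autistic adults as an audience for the messages and for the evaluation of the training.

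**Working it through.** No power or error-rate formula applies. The check is to compare the statements and count the places concerned.

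**1. The plan's own figure.** The criteria section says "We aim to recruit at least 120 participants, which we anticipate will yield a total of 96 participants in the final sample", allowing 20% attrition. 120 × (1 − 0.20) = 96, so the figure reproduces from 120. From the 120 + 120 = 240 in Recruitment Methods it would be 240 × 0.80 = 192, which does not match the 96 given there. That is a separate inconsistency, but it shows that the split pilot target is not secure.

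**2. ASD share of each target, as listed in Recruitment Methods.**

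| Target | ASD | IDD | Other | Total | ASD share |
|---|---|---|---|---|---|
| Interviews | 20 | 20 | 0 | 40 | 50% |
| Survey | 100 | 100 | 0 | 200 | 50% |
| Vector modeling and messaging | 10 | 10 | 20 | 40 | 25% |
| Pilot | 120 | 120 | 0 | 240 | 50% |
| Phase 2 focus groups | 0 | 30 | 30 | 60 | 0% |

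Interviews, survey and pilot together: 20 + 100 + 120 = 240 ASD places out of 40 + 200 + 240 = 480, or 50%. All four Phase 1 targets: 250 / 520 = 48%.

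**3. The same targets elsewhere.** Procedures gives interviews as n=20 (or to saturation) and the survey as n=100, each for ASD and IDD taken together. The criteria section and the randomization paragraph give the pilot as 120 in total, 40 per arm. On those figures the three targets come to 20 + 100 + 120 = 240 people with no ASD share stated. The 240 ASD places therefore rest on Recruitment Methods alone. Without the pilot split, that section still gives 20 + 100 = 120 ASD places.

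**4. The statements on whom to inform.**
- Eligibility: ASD or IDD.
- Agency instruction in the criteria section: IDD only.
- Administrators in Procedures: everyone who meets the criteria, hence ASD or IDD.

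The second cannot be followed together with the third unless IDD is taken to include ASD.

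**5. Size of the effect.** Let s be the share of an agency's ASD clients who have no IDD diagnosis. The documents do not give it. Under the literal instruction, of every 120 ASD clients who would otherwise be told, 120 × s are not: 0 if s = 0, 60 if s = 0.5, 120 if s = 1. These values of s are assumptions that show the range; none is an estimate.

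**The case against.** The strongest reply is that IDD is meant as an umbrella term that includes ASD. The official title, the abstract and the second research question speak only of IDD, and Vulnerable Populations describes the study population as people with developmental disabilities. Other sections join the two terms in several ways. On that reading the instruction excludes nobody. The reading is possible and cannot be ruled out from the text. However, the protocol never defines IDD in this way, and separate counts for ASD and IDD fit it poorly: an IDD group that included ASD would overlap the ASD group. If this meaning is intended, the definition is what is missing, and agencies still need it.

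The second reply is that one sentence should not outweigh two procedural statements that administrators inform everyone eligible, after which the coordinator determines inclusion. This stands in part. It means that the exclusion of ASD-only clients is a risk under one of two instructions and not a settled feature of the plan. It does not tell an agency which instruction to follow. The pilot paragraph only refers back to the recruitment sites and does not restate who is to be informed.

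The third reply is that nothing in the analysis turns on diagnosis: no stratification by diagnosis is described for the randomization, and Data Analysis names no comparison by diagnosis. That is correct. The instruction also acts before assignment and so falls on all three arms alike. What is at stake is who the results describe, not the fairness of the comparison between arms.

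**Conclusion.** The point holds as a wording inconsistency of minor weight. The Phase 1 agency instruction is narrower than the eligibility rule, conflicts with the direction to administrators, and sits badly with the separate ASD targets. The places concerned number up to 240 by Recruitment Methods. The number of people who would be missed is unknown.

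This rests on two assumptions: that agencies apply the instruction as written, and that IDD does not already include ASD.

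A reader might infer three stronger things that the documents do not support:
- That half of every target is ASD. It is 10 of 40 in vector modeling and messaging (half of the 20 participants with a disability there) and 0 of 60 in the Phase 2 focus groups, and other sections give no split.
- That people with ASD will be shut out. The Procedures text points the other way, and the umbrella reading remains open.
- That Phase 2 repeats the Phase 1 conflict with an ASD quota. Phase 2 has no such quota. Its IDD-only instruction agrees with its target of 30 people with IDD, and the statement that differs is the ASD or IDD eligibility rule.

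**What to change.** Phase 1, in the Inclusion and Exclusion Criteria:
- Change the agency instruction so that it covers a diagnosis of ASD or IDD, in line with the eligibility rule and with Procedures. Bring the following sentence on documented disabilities into line.
- Alternatively, state once that IDD includes ASD. The separate targets would then need labels that do not overlap.
- State in which group a person with both diagnoses is counted. The demographic form already collects primary and other diagnosis, so no new item is needed for the pilot. The form is tied to the pre-test, so confirm that the same information is recorded for interviews and survey.
- If agencies have already recruited, record which instruction they applied.

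Phase 2: decide whether people with ASD alone are meant to take part, then make the eligibility rule, the agency instruction and the target of 30 people with IDD agree. Changing the instruction alone would leave the target unreconciled.

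The cost is a few sentences in a protocol amendment and a note to the agencies. No sample size, procedure or analysis changes.

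### The Phase 1 timeline counts about 120 completers, but the randomisation target is 120 randomised, which the plan's own 20% attrition reduces to about 96

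*Combined protocol and SAP*

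**What the plan says.** Four places in section 9 (Study Design) bear on the Phase 1 trial size.

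- **Study Timelines, Phase 1:** in years two and three, SAFE is to be delivered "until approximately 120 participants have completed the program and data collection". The next sentence deals with recruitment: "Recruitment will occur throughout the course of the study until the targeted number of participants is obtained". It gives no number.
- **Study Procedures and Data Analysis:** "We will randomize in blocks of 12 (4 to each group) until we reach the targeted number of 120", which the same sentence equates with "40 participants in each group". The groups are peer support, staff delivery and control.
- **Inclusion and Exclusion Criteria:** "We aim to recruit at least 120 participants, which we anticipate will yield a total of 96 participants in the final sample", after allowing for 20% attrition.
- **Recruitment Methods, Phase 1:** at least 120 people with ASD and 120 with IDD for the SAFE pilot, with the same expected final sample of 96.

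Controls are not given SAFE: "The control group will continue to receive their standard vocational rehabilitation supports". The documents contain no power calculation, significance level, effect size or standard deviation that would show which number drives the design.

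**The concern.** The figure 120 is a count of finishers in the timeline and a count of people randomised in Study Procedures. With 20% attrition planned, these are different trials. A team working from the timeline would expect about 120 people with complete data. A team working from Study Procedures would stop randomising at 120 and expect about 96.

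The number randomised, the number analysed and the precision of each between-arm comparison depend on which is meant. That includes the third research question, peer support against staff delivery. If the completer count governed, the final size would also depend on the dropout observed.

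The unit counted in the timeline is unclear as well. Control participants have no program to complete, so a count of people finishing the program does not obviously include them.

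**Working it through.** **Inputs from the documents**
- Attrition d = 0.20 and expected final sample 96 (Inclusion and Exclusion Criteria).
- Target 120, three equal groups of 40, blocks of 12 with 4 per group (Study Procedures).
- About 120 completers (Study Timelines, Phase 1).

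**Step 1. Reproduce the plan's figure.** Completers = N × (1 − d) = 120 × 0.80 = 96. This matches. Also 120 / 12 = 10 full blocks and 120 / 3 = 40 per group, so Study Procedures and Inclusion and Exclusion Criteria agree with each other. Completers per arm = 40 × 0.80 = 32.

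**Step 2. Take the timeline's 120 as completers.** N = 120 / (1 − 0.20) = 150 randomised, or 50 per arm. Then 150 / 12 = 12.5 blocks; 13 whole blocks give 13 × 12 = 156. Completers are 120 at N = 150 (40 per arm) and 156 × 0.80 = 124.8 at N = 156. The excess over Study Procedures is 150 − 120 = 30 to 156 − 120 = 36 people.

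**Step 3. Can the word approximately cover the gap?** Completers from 120 randomised, by attrition:

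| Attrition | Completers |
|---|---|
| 2% | 117.6 |
| 3% | 116.4 |
| 5% | 114 |
| 10% | 108 |
| 20% (planned) | 96 |

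The two counts nearly coincide only at attrition of about 2 to 3%. At the planned rate the shortfall is (120 − 96) / 120 = 20%.

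**Step 4. Effect on precision.** Assumptions: 20% loss in each arm, a common SD, no covariate adjustment, two-sided 95% interval for the difference between two arms. In SD units, half-width = t(0.975, 2n − 2) × √(2/n).

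- n = 32 per arm: t with 62 df ≈ 2.00; √(2/32) = 0.250; half-width ≈ 0.50 SD.
- n = 40 per arm: t with 78 df ≈ 1.99; √(2/40) = 0.224; half-width ≈ 0.45 SD.

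**Step 5. The remaining figure.** Recruitment Methods gives 120 + 120 = 240 recruited. At 20% attrition that is 240 × 0.80 = 192, not the 96 stated there.

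**The case against.** The strongest reply is that the timeline sentence is not an enrolment rule. It says how long the team intends to deliver the program, and it is hedged. The timeline's recruitment sentence comes next and stops at the targeted number; Study Procedures uses the same term and sets it at 120. On that reading there is one enrolment rule, 120 randomised, beside a loosely worded sentence about delivery. This largely stands. A reader might infer that the protocol contains two competing rules for ending enrolment, but the documents do not support that. Nor is the figure under Inclusion and Exclusion Criteria a stopping rule: it is worded as a minimum, and it supplies the 96 and the 20%. What survives is that the completer count, as written, does not fit the other two sections, and Step 3 shows that the hedge does not bridge a 20% gap.

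Two further inferences should be resisted.

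- Because controls have no program to finish, a reader might count 120 program completers from the two SAFE arms alone. That would mean 120 / 0.80 = 150 in two arms, 75 per arm and 225 in three arms (18.75 blocks, so 228 in whole blocks). No section describes such a trial, and Study Procedures spreads its 120 over all three groups. The useful residue is only that the unit counted should be defined.
- A reader might fear that stopping mid-block destroys the equal allocation. With 4 per group in a block, one unfinished block can make two arms differ by at most 4, against about 50 per arm.

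**Conclusion.** The point holds as an inconsistency in a stated sample-size figure. At the plan's own 20% attrition, 120 randomised gives about 96 completers (32 per arm), while 120 completers needs 150 randomised, or 156 in whole blocks. The timeline's completer count is the likely outlier, because its recruitment sentence and the matching figures in Study Procedures and Inclusion and Exclusion Criteria all point to 120 randomised.

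The effect on precision is modest: about 0.50 SD against 0.45 SD for peer versus staff, under the assumptions in Step 4. The documents state no power target, so neither size can be called inadequate on this ground. The correction is still worth making, because the text does not let a reader establish the intended number of completers with certainty.

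**What to change.** Restate the sentence under Study Timelines, Phase 1, along these lines: *Enrolment ends when 120 participants have been randomised (10 blocks of 12, 40 per group); about 96 are expected to have a post-test.* Counting people with a post-test, rather than people who finished the program, brings the controls into the count.

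If 120 completers is the true target, leave that aim in the timeline and restate Study Procedures and Inclusion and Exclusion Criteria instead, with 150 to 156 randomised. The choice is the sponsor's. If Phase 1 enrolment has already closed, state which count was applied.

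Reconcile Recruitment Methods, Phase 1, in the same edit, since its 120 ASD plus 120 IDD is also said to yield 96. Changing the timeline alone would leave 240 in the protocol.

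The cost is a few lines of text. Under the first option, the stated number of completers falls from about 120 to about 96. Under the second, 30 to 36 more people must be randomised.
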